5.1 Full Analysis Set (FAS)

The FAS consists of all subjects who are randomized and receive at least 1 dose of double-blind study drug and have a Baseline micturition measurement and at least 1 post-Baseline micturition measurement.

5.2 Per Protocol Set (PPS)

The PPS includes all subjects of the FAS who do not meet criteria for exclusion from PPS listed in section 5.2.1 of the SAP.

5.2.1 Reasons for Exclusion From PPS

Subjects in FAS who meet any of the following criteria will be excluded from PPS:

1. Those subjects who violated the inclusion criteria.
2. Those subjects who violated the exclusion criteria.
3. Those subjects with drug compliance during the Screening period and Treatment period of less than 80%.
4. Those subjects who took the study drug for less than 42 days from the day following dispensing during the Treatment period. However, subjects who discontinued the study for efficacy-related reasons, such as insufficient therapeutic effect, will be included in the PPS, even if the drug was taken for less than 42 days.
5. Subjects without diary entries for at least 2 of the 3 consecutive days at Visit 2 and the last visit during the Treatment period.
6. Subjects who received any of the prohibited concomitant medications/therapies that may affect the evaluation of efficacy.

5.3 Safety Analysis Set (SAF)

The SAF consists of all subjects who received at least 1 dose of double-blind study medication.

6 ANALYSIS VARIABLES

6.1 Efficacy Endpoints

6.1.1 Primary Efficacy Endpoint

The primary endpoint is the change from Baseline to End of Treatment in the mean number of micturitions in 24 hours, based on a 3-day micturition diary.

For each patient, the mean number of micturitions per 24 hours will be calculated by taking the sum of all marked episodes in the patient diary where the variable 'Urinated' is indicated, divided by the number of days on which episodes were marked in the column 'Urinated'.

A diary day will cover information from 6:00 AM to 5:59 AM the following morning, consequently both date and time of the episodes recorded need to be considered when assessing the number of days on which episodes were marked.

The mean number of micturitions/24 hours in the 3-day diary period before baseline (Visit 2) will be regarded as the baseline value.

6.1.2 Secondary Efficacy Endpoints

The secondary endpoints include the change from Baseline to post-baseline and End of Treatment in:

- Mean number of micturitions/24 hours (except for End of Treatment visit)
Calculation is same as the primary endpoint.
- Mean number of urgency episodes/24 hours

Calculation is similar to ‘micturition’, but sum episodes in the diary where the variable ‘Urgency’ is indicated. The calculation of days is as per ‘micturition’. If there is no urgency episodes on all evaluable days in each visit, then the mean number of urgency episodes/24 hours is equal to zero. Only those subjects whose symptoms were confirmed at baseline (Visit 2) will be analysed, therefore if the mean number of urgency episodes per 24 hours is “0” at baseline, this subject is excluded from the analysis.

- Mean number of urgency incontinence episodes/24 hours
Calculation is similar to ‘micturition’, but sum episodes in the diary where both the variables ‘Urgency’ and ‘Urinary incontinence’ are indicated. Only those subjects whose symptoms were confirmed at baseline (Visit 2) will be analysed. If there is no urgency incontinence episodes on all evaluable days in each visit, then the mean number of urgency incontinence episodes/24 hours is equal to zero. Therefore if the mean number of urgency incontinence episodes per 24 hours is “0” at baseline, this subject is excluded from the analysis.

- Mean number of incontinence episodes/24 hours
Calculation is similar to ‘micturition’, but sum episodes in the diary where the variable ‘Urinary incontinence’ is indicated. Only those subjects whose symptoms were confirmed at baseline (Visit 2) will be analysed. If there is no incontinence episodes on all evaluable days in each visit, then the mean number of incontinence episodes/24 hours is equal to zero. Therefore if the mean number of incontinence episodes per 24 hours is “0” at baseline, this subject is excluded from the analysis.

- Mean number of nocturia episodes
Calculation is similar to ‘micturition’, but sum episodes in the diary where the variable ‘Urinated’ is indicated during the night time excluding the same time recorded as the time of sleep onset, divided by the number of nights. If the interval between sleep onset time and wake up datetime is more than 24 hours, then the records during the interval will not be used as nocturia.
Night time is the period between after sleep onset time and the wake-up time the following day (micturitions at the same time as the wake-up time will be excluded). The diary must be completed for at least 2 consecutive days to allow assessment of night time frequency for at least 1 night. Any data collected before the wake-up time on the first day of diary completion and after the sleep onset time on the third day cannot be included in the assessment of night time frequency. Only those subjects whose symptoms were confirmed at baseline (Visit 2) will be analyzed.
If there is no nocturia episode on all evaluable night time in each visit, then the mean number of nocturia episodes/24 hours is equal to zero. Therefore if the mean number of nocturia episodes per 24 hours is “0” at baseline, this subject is excluded from the analysis.

- Mean volume voided per micturition
Calculation is similar to ‘micturition’, but sum urinary volumes where the volume voided is > 0 and where ‘Urinary incontinence’ is not indicated, rather than count the episodes. The denominator will be the number of micturitions where the volume voided is > 0 and where ‘urinary incontinence’ is not indicated. Only those subjects whose symptoms were confirmed at baseline (Visit 2) will be analysed.

- Total OABSS score
For each patient, OABSS total score will be the sum total of the score of each item (Questions 1-4).
- Subscale scores (daytime frequency, nighttime frequency, urgency and urgency incontinence) from OABSS score
For each patient, OABSS subscale scores will be the score of each item (Questions 1-4).
- Total IPSS score
For each patient, total IPSS score will be the sum total of the score of each item (Questions 1-7).
- Subscale scores (storage subscale, voiding subscale-1, voiding subscale-2 and quality of life item) and individual scores from IPSS score
For each patient, IPSS subscale scores will be calculated by following each formula. Storage subscale is derived as sum of scores for questions 2, 4, and 7. Voiding subscale-1 is derived as sum of scores for questions 3, 5, and 6. Voiding subscale-2 is derived as sum of voiding subscale-1 and the score for question 1.
For each patient, Individual scores and IPSS QoL score will be the score of each item (Questions 1-7 and quality of life item).

- Symptom Bother and Total Health-Related Quality of Life scores (Total HRQL scores), as assessed by OAB-q

For each patient, OAB-q score (Symptom Bother and Total HRQL score) will be calculated by following each formula.

Symptom Bother is derived as sum of scores for questions 1-8; lowest possible raw score: 8; highest possible raw score: 48; possible raw score range: 40.

$$\text{Symptom Bother} = \frac{(\text{Actual raw score} - \text{lowest possible raw score})}{\text{Possible raw score range}} \times 100$$

Higher Symptom Bother is indicative of greater symptom bother.

Total HRQL score is derived as sum of HRQL subscale scores (not individual items); lowest possible raw score: 25; highest possible raw score: 150; possible raw score range: 125.

$$\text{Total HRQL score} = \frac{(\text{Highest possible raw score} - \text{Actual raw score})}{\text{Possible raw score range}} \times 100$$

Higher total HRQL score is indicative of better HRQL.

For the subscale analyses, if < 50% of the scale items are missing, the scale should be retained with the mean scale score of the items present used to impute a score for the missing items. If >= 50% of the items are missing, no scale score should be calculated and the subscale score should be considered missing. If any subscale score (refer to section 6.1.3 for detail) is missing, the HRQL Total score cannot be calculated.

Subjects should be instructed to complete the 3-day micturition diary on the 3 days leading up to the visit for Visit 2 (Day 1), Visit 3 (Day 29 ± 7 days), Visit 4 (Day 57 ± 7 days), and Visit 5 (Day 85 ± 7 days). If the subject is unable to fill out the diary on the 3 days prior to the visit, then the diary should be completed on any 3 days within the 7 days prior to the visit.

Subjects will complete the OABSS and IPSS/IPSS (QoL) assessments at Visit 1 to Visit 5.

Subjects will complete the OAB-q at Visit 1, Visit 2, and Visit 5.

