6.1.3 Exploratory Efficacy Endpoints

The exploratory endpoints will include the change from Baseline to post baseline and End of Treatment in:

- Hours of undisturbed sleep (HUS)

For each patient, hours of undisturbed sleep (HUS) will be calculated by visit and night. Only those subjects whose symptoms were confirmed at baseline (Visit 2) will be analyzed, therefore if IPSS Q7 score is “0” at baseline, this subject is excluded from the analysis.

HUS is calculated as time from sleep onset time to time of first micturition episode (the variable ‘Urinary incontinence’ or ‘Urgency’ is NOT indicated and after the time of sleep onset time) only if the diary completed for 3 consecutive days is available. On the other hand, for those subjects who have no micturition episode between after sleep onset time and wake up time, HUS is calculated as time from sleep onset time to wake up time.

If the interval between sleep onset time and wake up time is more than 24 hours, HUS will be calculated as follows:

HUS is calculated as time from sleep onset time to time of first micturition episode (the variable ‘Urinary incontinence’ or ‘Urgency’ is NOT indicated and after the time of sleep onset time) only if the diary completed for 3 consecutive days is available and the time of first micturition episode is before AM.5:59 of the next day of sleep onset. On the other hand, for those subjects who have no micturition episode between after sleep onset time and AM.5:59 of the next day, HUS is null.

- First nighttime voided volume

For each patient, urinary volume at the first nighttime (between after the time of sleep onset and wake up time + 30 minutes) will be calculated. Only those subjects whose symptoms were confirmed at baseline (Visit 2) will be analysed.

If the interval between sleep onset time and wake up time is more than 24 hours, first nighttime voided volume will be calculated as follows:

For each patient, urinary volume at the first nighttime (after the time of sleep onset and before AM.5:59 of the next day) will be calculated. On the other hand, for those subjects who have no micturition episode between after sleep onset time and AM.5:59 of the next day, urinary volume at the first nighttime is null. Only those subjects whose symptoms were confirmed at baseline (Visit 2) will be analysed.

- Subscale scores (coping, concern, sleep and social interaction) and individual scores from OAB-q scores

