For each patient, OAB-q subscales will be calculated similar to Total HRQL score.

Coping is derived as sum of scores for questions 9, 11, 16, 21, 22, 26, 32, and 33.

Concern is derived as sum of scores for questions 12, 13, 14, 19, 23, 25, and 29.

Sleep is derived as sum of scores for questions 10, 15, 17, 24, and 30. Social

interaction is derived as sum of scores for questions 18, 20, 27, 28, and 31.

- Normalization rate of OABSS
For each patient, normalization according to OABSS score will be classified by following criteria.
 - Normal: OABSS total score ≤ 2 or the score of Questions 3 ≤ 1
 - Not-normal: OABSS total score ≥ 3 and the score of Questions 3 ≥ 2
- Normalization rate of micturition diary (number of episodes of micturition/urgency/urgency incontinence/incontinence/nocturia)
For each patient, normalization according to symptom derived from the patient diary will be classified by following criteria.
For micturitions,
 - Normal: mean number of micturitions per 24 hours < 8
 - Not-normal: mean number of micturitions per 24 hours ≥ 8For urgency episodes, incontinence episodes, urgency incontinence episodes and nocturia,
 - Normal: mean number of each symptom per 24 hours is equal to zero.
 - Not-normal: mean number of each symptom per 24 hours > 0

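### For nights recorded as longer than 24 hours, the SAP removes the voids from nocturia without saying that the night leaves the divisor, and drops long undisturbed-sleep times selectively

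*SAP*

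**What the plan says.** SAP 6.1.2 counts voids "during the night time excluding the same time recorded as the time of sleep onset, divided by the number of nights". It defines the night as follows: "Night time is the period between after sleep onset time and the wake-up time the following day". Diary data before the first wake-up and after the third sleep onset are not used, so a 3-day diary yields at most two nights. One night is enough for a value.

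When the interval from sleep onset to wake-up is longer than 24 hours, "then the records during the interval will not be used as nocturia". The sentence is about the records and does not mention the night itself.

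Two further rules act on the result. The mean is set to 0 when no episode is left on any evaluable night. And "if the mean number of nocturia episodes per 24 hours is “0” at baseline, this subject is excluded from the analysis". For normalisation, SAP 6.1.3 classifies nocturia thus: "Normal: mean number of each symptom per 24 hours is equal to zero". Protocol 7.4.3 uses the same criterion.

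SAP 6.1.3 treats the same kind of night differently. HUS runs to the first void that is not flagged as urgency or incontinence, provided that it falls before 05:59 and that all three diary days are complete. Otherwise, "for those subjects who have no micturition episode between after sleep onset time and AM.5:59 of the next day, HUS is null". The same 05:59 cut-off applies to first nighttime voided volume. On an ordinary night without a void, HUS is scored up to wake-up, and SAP 7.4.3 censors it there in the Kaplan-Meier analysis.

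**The concern.** Barring the records is understandable, because an interval of more than 24 hours takes in daytime voids. But if the voids leave the numerator and the night stays in the divisor, a night that could not be assessed is scored as a night with no nocturia. With at most two nights per visit, one such night is half or all of the data.

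A resulting zero is not neutral. At baseline it removes the man from the nocturia analysis; afterwards it is the best possible outcome. Change in nocturia is a secondary endpoint, tested by ANCOVA in the FAS and PPS under SAP 7.4.2.

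For HUS, whether an affected night is used depends on its outcome. A night with an early qualifying void is kept, and one without is discarded. The average then rests disproportionately on short values, and an arm with more uninterrupted nights would lose more of its best results.

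**Working it through.** The plan states no figure on this point, so there is none to reproduce. The check applies the SAP formula under the two possible readings of the divisor. The void counts are assumed for illustration.

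**Nocturia, two diary nights.** Let the normal night have *a* voids and the night recorded as over 24 hours have *b* genuine night voids.

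- Voids removed, night kept: (a + 0)/2 = a/2
- Voids and night both removed: a/1 = a
- All genuine night voids counted: (a + b)/2
- Shortfall if the night is kept: (a + b)/2 − a/2 = b/2, so 0.5 to 1.5 for b = 1 to 3

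| a | b | Night kept | Night removed | All night voids |
|---|---|---|---|---|
| 2 | 2 | 2/2 = 1.0 | 2/1 = 2.0 | 4/2 = 2.0 |
| 3 | 1 | 3/2 = 1.5 | 3/1 = 3.0 | 4/2 = 2.0 |
| 0 | 2 | 0/2 = 0 | 0/1 = 0 | 2/2 = 1.0 |

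**Nocturia, only the affected night available.** Night kept: 0/1 = 0. Night removed: 0/0, which is missing. If both of two nights are affected, the results are 0/2 = 0 and missing.

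**Effect on change from baseline.** Take a man with a true mean of 2.0 at both visits (true change 0) and one affected night out of two, kept in the divisor.

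- Affected night at End of Treatment: 1.0 − 2.0 = −1.0, a false improvement
- Affected night at baseline: 2.0 − 1.0 = +1.0, a false worsening

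**HUS, rule against rule.** Let *s* be the sleep-onset time.

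| Night | Qualifying first void before 05:59 | No qualifying void by 05:59 |
|---|---|---|
| Ordinary | Time from s to the void | Time from s to a later qualifying void, or to wake-up |
| Over 24 hours | Time from s to the void | Null |

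In the second row, every retained value is shorter than the time from s to 05:59. Every discarded night had undisturbed sleep, as HUS defines it, of at least that length. Whether a value is kept therefore depends on the value itself.

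**The two sections together.** A night over 24 hours with an unflagged void 3 hours after sleep onset gives HUS = 3 h under SAP 6.1.3. Under SAP 6.1.2 it contributes no nocturia.

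**The case against.** The strongest reply is that the SAP does not say that the night is kept. A reader might infer a stated rule that deletes voids while retaining the night. The text does not go that far: it is silent, and the zero rule refers to evaluable night time, which can be read as leaving such a night out. SAP 7.10 also defers details to a data specification document that is not supplied. This stands as a limit on the claim, but it does not settle the matter. Evaluable is not defined for these nights, and the word does not appear in the division. For mean volume voided, the same section repeats its restriction for the denominator; for nocturia it does not. A programmer following the wording would keep the night.

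Other stronger readings also fail:

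- **HUS does not reuse all the voids barred from nocturia.** It uses only the first unflagged void before 05:59, and only with a complete diary.
- **The nights lost are not only undisturbed ones.** A first void after 05:59 also leads to null, and early voids that are all flagged do not qualify as the end of HUS.
- **Early risers are not shown to be caught systematically.** One might infer this by reading the following day as the 06:00 to 05:59 diary day. The over-24-hour rule refers to a wake-up datetime, which points to ordinary clock intervals.
- **No net bias in favour of either arm follows.** The rule is the same in both arms, and the error changes sign with the visit.

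It is also fair that the diary is reviewed with the subject at each visit (Table 1, footnote j) and unclear entries are queried (Protocol 8.1.1), which should make such nights less common. HUS and normalisation are described without a between-arm test.

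**Conclusion.** The concern holds in limited form. The nocturia divisor is unspecified for nights over 24 hours. On the literal reading, the visit mean is too low by b/2 when one of two nights is affected (1.0 instead of 2.0 in the example), and a sole affected night becomes a false zero if it contained voids. The error in an individual's change is −1.0 or +1.0 in that example, depending on whether the affected night falls at End of Treatment or at baseline. Separately, and without depending on that reading, the HUS rule for such nights selects on outcome and discards long values.

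The size at trial level cannot be computed, because the documents do not give the frequency of such nights. The sponsor did foresee them, since the SAP has a rule for them under nocturia, HUS and first nighttime voided volume. The consequences are confined to one secondary endpoint (nocturia) and to exploratory ones (HUS and nocturia normalisation). The primary endpoint counts voids by diary day and is untouched. This should be corrected before unblinding, but it does not threaten the main conclusion.

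**What to change.** 1. **SAP 6.1.2, end of night.** State that each night ends at the first recorded wake-up datetime after sleep onset.
2. **SAP 6.1.2, nocturia.** State that a night over 24 hours is not evaluable and leaves both numerator and denominator. If no evaluable night remains, nocturia is missing, not zero, for the change, the baseline exclusion and normalisation alike.
3. **SAP 6.1.3 and 7.4.3, HUS.** In the Kaplan-Meier analysis, keep a qualifying void before 05:59 as an event and censor at 05:59 when there is none. In the mean analysis, set HUS to missing for every such night, whether or not a void occurred. Say how the Kaplan-Meier variant that counts undisturbed nights as events at wake-up will treat these nights.
4. **First nighttime voided volume.** Confirm whether the 05:59 cut-off stays.

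HUS and nocturia may still use different nights. That is defensible: HUS needs only the first void, while a nocturia count needs the whole night.

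The cost is a few lines of SAP text and derivation code, and a few nights or subjects become missing. Removing a night does not recover its voids: with 3 voids on the valid night and 1 on the affected night, the mean is 3.0 instead of 2.0, and with 0 and 2 it is 0 instead of 1.0. It does stop an unassessable night from being scored as a night without nocturia. Reporting the number of such nights by arm and visit would show whether the rule mattered.

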6.1.3 Exploratory Efficacy Endpoints

The exploratory endpoints will include the change from Baseline to post baseline and End of Treatment in:

- Hours of undisturbed sleep (HUS)

For each patient, hours of undisturbed sleep (HUS) will be calculated by visit and night. Only those subjects whose symptoms were confirmed at baseline (Visit 2) will be analyzed, therefore if IPSS Q7 score is “0” at baseline, this subject is excluded from the analysis.

HUS is calculated as time from sleep onset time to time of first micturition episode (the variable ‘Urinary incontinence’ or ‘Urgency’ is NOT indicated and after the time of sleep onset time) only if the diary completed for 3 consecutive days is available. On the other hand, for those subjects who have no micturition episode between after sleep onset time and wake up time, HUS is calculated as time from sleep onset time to wake up time.

If the interval between sleep onset time and wake up time is more than 24 hours, HUS will be calculated as follows:

HUS is calculated as time from sleep onset time to time of first micturition episode (the variable ‘Urinary incontinence’ or ‘Urgency’ is NOT indicated and after the time of sleep onset time) only if the diary completed for 3 consecutive days is available and the time of first micturition episode is before AM.5:59 of the next day of sleep onset. On the other hand, for those subjects who have no micturition episode between after sleep onset time and AM.5:59 of the next day, HUS is null.

- First nighttime voided volume

For each patient, urinary volume at the first nighttime (between after the time of sleep onset and wake up time + 30 minutes) will be calculated. Only those subjects whose symptoms were confirmed at baseline (Visit 2) will be analysed.

If the interval between sleep onset time and wake up time is more than 24 hours, first nighttime voided volume will be calculated as follows:

For each patient, urinary volume at the first nighttime (after the time of sleep onset and before AM.5:59 of the next day) will be calculated. On the other hand, for those subjects who have no micturition episode between after sleep onset time and AM.5:59 of the next day, urinary volume at the first nighttime is null. Only those subjects whose symptoms were confirmed at baseline (Visit 2) will be analysed.

- Subscale scores (coping, concern, sleep and social interaction) and individual scores from OAB-q scores

For each patient, OAB-q subscales will be calculated similar to Total HRQL score.

Coping is derived as sum of scores for questions 9, 11, 16, 21, 22, 26, 32, and 33.

Concern is derived as sum of scores for questions 12, 13, 14, 19, 23, 25, and 29.

Sleep is derived as sum of scores for questions 10, 15, 17, 24, and 30. Social

interaction is derived as sum of scores for questions 18, 20, 27, 28, and 31.

- Normalization rate of OABSS
For each patient, normalization according to OABSS score will be classified by following criteria.
 - Normal: OABSS total score ≤ 2 or the score of Questions 3 ≤ 1
 - Not-normal: OABSS total score ≥ 3 and the score of Questions 3 ≥ 2
- Normalization rate of micturition diary (number of episodes of micturition/urgency/urgency incontinence/incontinence/nocturia)
For each patient, normalization according to symptom derived from the patient diary will be classified by following criteria.
For micturitions,
 - Normal: mean number of micturitions per 24 hours < 8
 - Not-normal: mean number of micturitions per 24 hours ≥ 8For urgency episodes, incontinence episodes, urgency incontinence episodes and nocturia,
 - Normal: mean number of each symptom per 24 hours is equal to zero.
 - Not-normal: mean number of each symptom per 24 hours > 0

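### On its plain reading, SAP 6.1.3 ends hours of undisturbed sleep only at a night void without an urgency or incontinence flag, and nights with only flagged voids have no stated value

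*SAP*

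**What the plan says.** SAP 6.1.3 gives the standard rule in two parts. The first begins "HUS is calculated as time from sleep onset time to time of first micturition episode (the variable". Its bracket then sets the condition that a mark for leakage or for urgency "is NOT indicated and after the time of sleep onset time"; the diary must also cover 3 consecutive days. Second, "for those subjects who have no micturition episode between after sleep onset time and wake up time", HUS runs to wake-up. For a sleep-to-wake interval over 24 hours, the first part repeats the flag condition and adds a 5:59 AM limit. The second part says that with "no micturition episode between after sleep onset time and AM.5:59 of the next day, HUS is null". Neither second part mentions flags.

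SAP 7.4.3 describes HUS, and its Kaplan-Meier censoring at wake-up, by the presence or absence of a micturition episode, again without flags.

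Protocol 2.3.3 lists HUS as an exploratory endpoint, defined as change from Baseline to End of Treatment. SAP 7.4.3 summarises actual values and changes with descriptive statistics, plots and Kaplan-Meier estimates. It plans no between-group test for HUS.

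**The concern.** Waking to void with urgency disturbs sleep. A rule that passes over such a void measures time to the first void without a flag, which is a different quantity. Protocol 3.2 requires an average of at least 2 urgency episodes per 24 hours at entry, so flagged night voids are to be expected.

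Two things are at stake. One is the meaning of the reported HUS values. The other is reproducibility: two programmers could derive different HUS datasets from the same text, because nights with only flagged voids have no stated event time, censoring time or value.

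**Working it through.** The documents give no HUS figure and no share of night voids that are flagged. There is therefore nothing to reproduce, and every size below is an illustration.

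**1. Definitions side by side**
- Nocturia (SAP 6.1.2) counts every record where 'Urinated' "is indicated during the night time excluding the same time recorded as the time of sleep onset, divided by the number of nights". It has no flag condition.
- First nighttime voided volume (SAP 6.1.3): "urinary volume at the first nighttime (between after the time of sleep onset and wake up time + 30 minutes) will be calculated". It has no flag condition.
- Mean volume voided (SAP 6.1.2) leaves out incontinence-flagged records but not urgency-flagged ones. That exclusion implies that real voids can carry the incontinence flag.
- HUS skips both kinds of flagged record. One night can thus hold a nocturia episode and a first night void that HUS ignores.

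**2. The rule applied to invented nights** (sleep onset 0 h, wake-up 8 h)

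| Night | Plain reading | Condition carried into the no-void branch | Only both-flag voids skipped | Any void ends HUS |
|---|---|---|---|---|
| No void | 8 | 8 | 8 | 8 |
| Unflagged void at 3 h | 3 | 3 | 3 | 3 |
| Urgency void at 2 h, unflagged at 5 h | 5 | 5 | 2 | 2 |
| Urgency void at 2 h only | undefined | 8 | 2 | 2 |
| Incontinence void at 2 h only | undefined | 8 | 2 | 2 |
| Void at 2 h with both flags, only | undefined | 8 | undefined | 2 |

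**3. Direction.** The first qualifying void cannot precede the first void, so a scored night is never too short. The mean can still go either way if flagged-only nights are left unscored. Suppose half the nights have one unflagged void at 2 h and half have one flagged void at 6 h. The true mean is (2 + 6)/2 = 4 h, but only the first half is scored, giving 2 h.

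**4. Between-arm difference.** Assumed: sleep T = 7.5 h; L = 2.0 (placebo) and 1.8 (mirabegron) voids per night; Poisson counts at uniform times; independent flags with share p; m = L(1−p).
- True mean = (T/L)(1−e^−L).
- A (flagged-only nights run to wake-up) = (T/m)(1−e^−m).
- B (flagged-only nights unscored) = [(T/m)(1−e^−m) − T·e^−m + T·e^−L] / [1 − e^−m + e^−L].

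True means are 3.75 × 0.8647 = 3.24 h and 4.1667 × 0.8347 = 3.48 h, a difference of +0.24 h. Flagged-only nights on placebo at p = 30% make up e^−1.4 − e^−2 = 0.247 − 0.135 = 11%.

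| Flagged share, placebo / mirabegron | A: means, difference (h) | B: means, difference (h) |
|---|---|---|
| 30% / 30% | 4.04, 4.26, +0.23 | 3.60, 3.83, +0.23 |
| 30% / 25% | 4.04, 4.12, +0.08 | 3.60, 3.76, +0.16 |

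**5. Change from Baseline within an arm.** Assume L falls from 2.2 to 2.0. With 30% flagged at both times, the true change is 3.243 − 3.031 = 0.211 h, against 4.036 − 3.826 = 0.210 h under A and 3.602 − 3.402 = 0.201 h under B. The bias is about −0.001 h and −0.01 h. If the share moves from 35% to 30%, the bias is −0.16 h (A) and −0.08 h (B).

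**The case against.** **The condition may mean something narrower.** It could mean that only voids with both flags are skipped. But for urgency incontinence SAP 6.1.2 says expressly that both variables must be indicated, whereas 6.1.3 says 'or'. Even so read, urgency-incontinence voids at night would be passed over. It could instead be meant to drop diary rows that are not voids, in which case there is no bias. The SAP selects voids elsewhere by the 'Urinated' variable: the primary endpoint is "calculated by taking the sum of all marked episodes in the patient diary where the variable" 'Urinated' is marked. SAP 6.1.3 does not use it. SAP 7.10 refers to a data specification document, not available here, which may settle the intent. This objection stands as uncertainty about intent; it does not repair the text.

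**The size is not known.** This stands. All inputs are assumed, and flag independence matters. If 30% of men had all their voids flagged, the overstatement of the placebo mean would be 1.28 h (A) or 0.23 h (B), against 0.79 h and 0.36 h with independent flags at 30%.

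**Stronger readings that the documents do not support.** A reader might infer that HUS is inflated in every arm with flagged voids. Step 3 shows that this fails when flagged-only nights go unscored, and an arm whose flagged voids always follow an unflagged one has no bias. A reader might also infer that the rule reverses the comparison. Under A with placebo at 30%, that needs a mirabegron share below 1 − 1.4/1.8 = 22.2%; under B it needs one below about 11.5% (solved numerically). The documents name the number of urgency episodes as an endpoint, but nothing in them says how treatment changes the share of night voids that are flagged.

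**Conclusion.** The text defect holds; its consequence is small. On the plain reading, both rules in SAP 6.1.3 pass over flagged night voids. Flagged-only nights have no stated value or censoring time; if the no-episode branch inherits the condition, the standard rule scores them as undisturbed to wake-up. Bias in change from Baseline largely cancels when the flagged share is stable, and the between-arm difference is materially distorted only if treatment changes that share. In the illustration, +0.24 h becomes +0.23 h at equal 30% shares and +0.08 to +0.16 h at 30% against 25%. These figures rest wholly on the assumed sleep length, void rates, flagged shares and independence. HUS is exploratory and untested between groups, so primary and secondary conclusions are unaffected. Severity: minor.

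**What to change.** Before unblinding, delete the flag condition from both rules in SAP 6.1.3. HUS then ends at the first 'Urinated' entry after sleep onset and before wake-up; the over-24-hour rule keeps its 5:59 AM limit and its null. Apply the same definition to the no-episode branch and to the descriptive and Kaplan-Meier censoring rules in 7.4.3. If the condition was meant only to drop rows that are not voids, the 'Urinated' criterion already does that.

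A separate and lesser point: the additional HUS subset in 7.4.3 is selected on a night void at baseline 'or/and post-baseline'. Read as 'and', it drops men whose nocturia resolved after randomization. Delete those words so that selection is on baseline only. The plan should also say which baseline criterion applies: 7.4.3 gives IPSS Q7 above zero only as an example, and 6.1.3 already excludes men on that item ("therefore if IPSS Q7 score is" zero at baseline), so that choice would simply repeat the main HUS population.

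The cost is a few lines of SAP wording and one programming condition. No new data are needed.
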